We will ask participants the average amount of money they spend each week on tobacco products; they will receive that balance for each mock (i.e., hypothetical) shopping trip, as is standard for ETM studies.³³ We will ask participants to imagine they were shopping in a convenience store, and to view six items available for purchase: preferred cigarillo brand, cigarette product (menthol and non-menthol), e-cigarette product (three variations), oral nicotine pouches, non-alcoholic drink, and snack food. They will be instructed to make hypothetical purchases of tobacco products that they would use for the week. In each shopping trip, the price of cigarillos will increase while those of alternative products remain the same. In each trial, participants can choose any combination of tobacco and non-tobacco products to ‘buy’, as long as they stay within their experimental budget. Across six mock shopping trips, the price of one of their preferred cigarillo products will increase from \$0.25, 0.50, \$0.75, \$1.50, \$3.00, \$6.00, based on an average price of \$0.91 per cigarillo.³⁴ Cigarette price will remain constant at \$6.00 per pack (\$0.30 per cigarette), e-cigarettes will be priced at \$4 per e-liquid pod or \$6 for 30 ml e-

liquid or \$12 for disposable device, and oral nicotine will be priced at \$4.00. Food and drink will be priced at \$2 each. Cigarillos will be purchased as singles to generate demand curves (see Measures and Analysis Plan).. This models other ETM studies.³³

After completing the hypothetical purchase tasks, we will assess additional constructs from our conceptual model. First, we will assess cigarillo warning label recognition (a measure of attention). We will then show the cigarillo warning to participants from their assigned experimental condition and ask them to respond to items assessing negative affect, thinking about the warnings, and intentions to quit using cigarillos.

At the end of this experiment, participants will view a **debriefing** page, including an explanation of the purpose of the study, emphasizing that the study is not promoting the use of cigarillos or any tobacco product and will include links to cessation services and information about the harms of cigarillo use. Participants will be compensated with 100 points (~\$2 value) by Kantar. These points can be used in exchange for a variety of items, including gift cards. We will not collect any identifying information such as name or birthdate.

Outcome Measure

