In exploratory analyses, to determine the extent to which each alternative product substituted for cigarillos, cross-price elasticities will be calculated as the slope of the regression line (B_1) fit to the log-transformed mean purchasing in mg of nicotine for each alternative tobacco product when offered at fixed prices (C) versus log-transformed cigarillo price (P): $\log C = B_0 + B_1 \log P$. Positive values indicate product substitution. We will use PRISM GraphPad Version 8.1.1 to generate the behavioral economics indices, demand curves, and cross-price elasticities. We will be able to determine if viewing a pictorial warning on a cigarillo resulted in substitution with another tobacco product without a pictorial warning, such as cigarettes or e-cigarettes, or a non-tobacco product, such as food or drink.

Every effort will be made to minimize the presence of missing data. Analyses will use all available data. Since missing data in a single item of a multi-item scale leads to a missing total, we will consider imputing both at the level of the item and scale total. Additionally, to evaluate the generalizability of our results, we will use t-tests and chi-squared tests to examine pairwise differences in characteristics between participants for whom we have complete data and those for whom we do not.

Human Subjects Protection

Subject Recruitment Methods

Kantar works with permission-based panels with 88 million respondents, including 21 million in the United States. Recruitment includes traditional advertising and through internal and external affiliate networks. Kantar uses a diverse set of sources to reduce panel bias. When recruiting participants into studies, Kantar engages in data validation to ensure quality respondents and

responses. Kantar will recruit participants, directly inviting them to participate in the experiment. Potential study participants will complete an eligibility screener for inclusion into the ETM study. Participants must be ages 21-34 and be current cigarillo users (use cigarillos at least one time per week for the past month). Further, because we are studying cigarillo warnings in the U.S., only those living in the U.S. are eligible. Kantar will also oversample for young adult Black/African American cigarillo users. Kantar oversamples by enrolling approximately 20% additional participants to the study.

Informed Consent

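### One straight log-log slope over six cigarillo prices can miss substitution above the market price if participants spend most of their balance and cigarillo spending peaks within the price range

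*Combined protocol and SAP*

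**What the plan says.** The cross-price analysis is the exploratory paragraph of the Analytic Plan in the combined protocol and SAP. The elasticity is the "slope of the regression line (B_1) fit to the log-transformed mean purchasing in mg of nicotine for each alternative tobacco product" on log cigarillo price, log C = B0 + B1 log P. The reading rule is "Positive values indicate product substitution". The plan has no check of linearity, no split at the market price, and no rule for a slope that is zero, negative or made up of a fall and a rise. The same paragraph says the study will be able to determine whether a pictorial warning led to substitution.

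The task is described under Interventions and Interactions. The balance is the participant's usual weekly tobacco spend, and "they will receive that balance for each mock (i.e., hypothetical) shopping trip". Participants may combine products freely "as long as they stay within their experimental budget". On each trip "the price of cigarillos will increase while those of alternative products remain the same". The cigarillo price "will increase from \$0.25, 0.50, \$0.75, \$1.50, \$3.00, \$6.00", "based on an average price of \$0.91 per cigarillo". Three of the six prices are therefore below the market average and three above it.

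Outcome Measure lists, among the secondary demand indices, the price of maximum purchasing and the money spent at that price. The plan thus allows for cigarillo spending that rises and then falls with price.

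**The concern.** With a constant balance and constant prices for alternatives, the money left for alternatives is the balance minus cigarillo spending. If cigarillo spending rises to a peak and then falls, that remainder shrinks and then grows. Participants who spend most of the balance would then produce a V-shaped relation between log alternative purchases and log cigarillo price. One straight line averages the two arms, and its sign depends on where the peak sits on the price grid.

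At stake is the statement made about each alternative. A near-zero or negative B1 for cigarettes, say, could be reported as no substitution even though cigarette purchases rise once cigarillos cost more than they do now. The background section presents the study as evidence for rulemaking on cigarillo warnings, and the range above the market price is the one closest to a measure that makes cigarillos less attractive.

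**Working it through.** The documents state no elasticity or expected slope, so there is no figure to reproduce. The check applies the plan's own regression to purchases generated from its own demand equation.

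**Inputs from the documents.** Prices $0.25, $0.50, $0.75, $1.50, $3.00 and $6.00; market average $0.91; the same balance each trip; constant prices for alternatives; the exponential demand equation (bracket read as part of the exponent).

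**Assumptions the documents do not give.** k = 1.5, 2 or 3; the price at which cigarillo spending peaks; cigarillos take 50% (or 30%) of the balance at $0.91; the whole remainder goes to alternative tobacco in a constant mix.

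**Step 1, cigarillo spending.** In units of Q0, with a = αQ0, `E(P) = P × 10^(k(exp(-aP) - 1))`. Spending peaks where `aP × exp(-aP) = 1/(k ln 10)`. For k = 2 the right side is 0.217, so aP = 0.290 at the peak. A peak at $1.50 gives a = 0.290/1.50 = 0.1935.

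**Step 2, share left for alternatives.** Balance B = E(0.91)/0.50; share A(P) = 1 - E(P)/B. For k = 2 and peak $1.50:
- E(0.91) = 0.433, so B = 0.865.
- E(1.50) = 0.470, so A = 1 - 0.543 = 0.457.
- E(6.00) = 0.254, so A = 1 - 0.293 = 0.707.

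Over the six trips the shares are:
- peak $1.50: 77, 62, 53, 46, 54, 71%. Alternatives rise by 0.707/0.457 - 1 = 55% from $1.50 to $6.00.
- peak $0.91: 69, 56, 51, 54, 69, 79%.

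**Step 3, least-squares slopes of log A on log P.**

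| k | Peak price | Cigarillo share at $0.91 | All six prices | $0.75 to $6.00 |
|---|---|---|---|---|
| 2 | $0.91 | 50% | +0.07 | +0.23 |
| 2 | $1.50 | 50% | -0.04 | +0.15 |
| 2 | $0.91 | 30% | +0.04 | +0.11 |
| 2 | $0.50 | 50% | +0.18 | +0.24 |
| 3 | $0.91 | 50% | +0.11 | +0.30 |
| 3 | $1.50 | 50% | -0.01 | +0.20 |
| 1.5 | $0.91 | 50% | -0.02 | +0.06 |
| 1.5 | $1.50 | 50% | -0.08 | +0.06 |
| 1.5 | $0.50 | 50% | -0.14 | -0.28 |

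In the last row the upper slope is the more negative one. With k = 1.5 the equation keeps consumption above 10^-1.5 of Q0 at any price, so cigarillo spending climbs again by $6.00 and the alternatives' share drops from 54% at $3.00 to 26%.

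Restricting to the three prices above $0.91, which double each time, the slope is `log(A(6.00)/A(1.50))/log 4`. For k = 2 this is log(0.793/0.544)/log 4 = +0.27 at peak $0.91 and log(0.707/0.457)/log 4 = +0.31 at peak $1.50.

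**Step 4, weaker assumptions.** If only half the freed money moves to alternatives (k = 2, 50% share), the slopes are +0.04 against +0.13 (peak $0.91) and -0.02 against +0.08 (peak $1.50). If the balance does not bind and alternatives simply replace lost cigarillos, alternatives rise at every price and the single slope is +0.28 to +0.31. An equal mix of spent and non-binding balances (k = 2, peak spending 70% of the balance) gives +0.20, +0.11 and -0.02 at peaks of $0.91, $1.50 and $3.00.

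**Step 5, where the sign turns.** With the balance fully spent, k from 2 to 4 and peak spending of 30% to 90% of the balance, the overall slope is zero at a peak of about $1.28 to $1.51 and negative above that. At a peak of $4 or more the slope from $1.50 upward is itself negative, so no upper-range substitution is missed.

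**The case against.** A reader might infer that the fixed balance forces purchases of alternatives to fall and then rise, so that a straight line is wrong for this design whatever the data. The documents do not support that. The balance is a ceiling, participants are asked to buy a week's use, and food and drink can absorb money. Nothing fixes where cigarillo spending peaks; planning to estimate a peak does not place it inside the grid. This objection stands, which is why the point is conditional.

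A reader might also infer that the plan treats a zero or negative slope as proof of no substitution. It does not say so; it interprets only positive values. What remains is that no rule covers the other outcomes, while the text says substitution can be determined.

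Nor is the upper-segment slope the true elasticity. In the model above, the fall and the rise are the same quantity, balance minus cigarillo spending, so one cannot be dismissed as budget arithmetic while the other is accepted as real switching. The planned B1 remains a legitimate average over the tested prices. A fixed knot at $0.75 has its own failure: with k = 2, a 50% share and a $3.00 peak, alternatives rise from 24% to 36% of the balance between $3.00 and $6.00, yet the slope from $0.75 is -0.24.

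Finally, the illustration pools all alternatives, whereas the plan fits each product separately. No pattern for a single product can be predicted from it.

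**Conclusion.** The concern holds conditionally. If most of the balance is spent and cigarillo spending peaks within $0.25 to $6.00, one slope over all six prices can be near zero or negative while purchases of alternatives rise clearly above the market price. At k = 2 with a 50% share, it understates the slope from $0.75 about threefold at a $0.91 peak (+0.07 against +0.23) and has the opposite sign at a $1.50 peak (-0.04 against +0.15). The gap is smaller with a 30% share or a low peak, slight at k = 1.5 with a $0.91 peak, and reversed at k = 1.5 with a $0.50 peak. With a balance that does not bind there is no problem. All of these sizes rest on assumed k, peak price, spending share and pass-through.

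The plan cannot know beforehand which situation will arise, and the single slope cannot tell a flat relation from a fall followed by a rise. Because the analysis is exploratory and does not touch the primary or secondary outcomes, this is a point to consider and not a required change.

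**What to change.** Keep the planned overall slope as a descriptive summary. For each alternative tobacco product, add:
- the six mean purchases, plotted or tabulated against cigarillo price;
- a check of curvature, for example a quadratic term in log P;
- separate slopes for the three prices below $0.91 and the three above it.

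Report the share of the balance spent on each trip, which shows whether the budget binds. State that a zero or negative overall slope alone is not evidence of no substitution. Do not make a fixed knot at $0.75 the sole decision rule.

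The cost is a few sentences in the Analytic Plan and a small amount of extra output from data already collected. The downside is imprecision: each segment slope rests on three means, and a quadratic term is fitted to six, so these results should be read alongside the plotted means and not as tests.

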The average total number of cigarillos purchased is the primary outcome.

We will assess secondary outcomes: average total amount (mg) of combusted and non-combusted tobacco purchased in the ETM.

In secondary analyses, we will also generate demand indices for cigarillos, including: demand intensity (consumption at the lowest cigarillo cost), demand elasticity (rate of change in demand for cigarillos), price of cigarillos resulting in maximum purchasing, the amount of money spent at the maximum purchasing price.

In exploratory analyses, we will assess cross-price elasticity measures, negative affect, cognitive elaboration (thinking about the warnings), intentions to quit using cigarillos, perceived message effectiveness, and warning recall/recognition, which is a measure of attention.

We will also measure several **covariates**: use of other tobacco products, cigarillo dependence, sexual orientation, race/ethnicity, socioeconomic status, sex, gender identity, and age.

Analytic Plan

This study will examine the impact of cigarillo warnings on purchasing behavior in a hypothetical shopping task using the online Experimental Tobacco Marketplace. The primary outcome is the average total amount of cigarillos “purchased” (hypothetical shopping task) compared across study conditions.

Baseline differences between participants (e.g., sex) across warning conditions will be examined using t-tests for continuous variables and χ^2 tests for categorical variables to evaluate randomization balance. The primary outcome, average total number of cigarillos purchased, will be modeled using random-effects linear regression models to account for the within-person correlation among the repeated measures represented by the six purchasing tasks. Warning condition will be included as a between-subjects fixed effect. Models will control for any variables that differ at baseline between conditions. We will also assess whether Black/African-American race moderates the effect of warning condition by including interaction terms between Black/African American race and warning condition. These same analyses will also be

conducted for our secondary outcomes for average total of mg combusted and non-combusted tobacco products.

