In secondary analyses, demand curves will be generated for each cigarillo warning condition in each of the ETM conditions using the exponential demand equation, $Q = Q_0 * 10^k(e^{-\alpha Q_0 C} - 1)$, where Q is the mg of nicotine purchased at a given price, Q_0 is peak demand consumption or intensity (typically occurring at the lowest price), k is a constant across all compared conditions, and alpha (α) is the rate of change in demand or elasticity.³⁵ To determine the extent to which pictorial warnings decrease cigarillo purchasing relative to the text-only warning conditions, the global fits of the demand curves for cigarillos from each condition will be compared using an extra-sum-of-squares F-test, which compares whether the fitted parameters (specifically, Q_0 and α) are significantly different across each curve. A significant difference in α would represent a difference in the essential value of the product, while a difference in Q_0 would indicate that purchasing was reduced in absolute terms but the underlying 'value' of the product was unchanged.^{36,37} Finally, each individual demand index will be compared across conditions using t-tests to determine if pictorial warnings affected specific indices of demand differentially. The number of cigarillos purchased is higher for text-only warnings compared to pictorial warnings at the same price, but demand overall will decrease as price increases.

Exploratory analyses will examine the effects of warning condition on other constructs in the conceptual model including negative affect, cognitive elaboration, behavioral intentions, and warning recall/recognition. Because these outcomes are measured only once after the completion of all six purchasing tasks, continuous outcomes will be modeled using standard linear regression modeling and categorical outcomes will be modeled using logistic and multinomial regression. All tests will be two-sided with a 0.05 significance level.

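### The plan promises to show whether the pictorial warning caused substitution, but its stated measure is a slope on cigarillo price with no comparison between warning conditions

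*Combined protocol and SAP*

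**What the plan says.** The cross-price analysis is in the exploratory part of the Analytic Plan. B1 is the slope of a line "fit to the log-transformed mean purchasing in mg of nicotine for each alternative tobacco product when offered at fixed prices", regressed on log cigarillo price: log C = B0 + B1 log P. The reading rule is "Positive values indicate product substitution". The same paragraph then states the conclusion to be drawn: "We will be able to determine if viewing a pictorial warning on a cigarillo resulted in substitution with another tobacco product", "or a non-tobacco product, such as food or drink".

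Elsewhere the Analytic Plan does compare conditions, but for other quantities:

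- Cigarillo demand: "demand curves will be generated for each cigarillo warning condition", and "the global fits of the demand curves for cigarillos from each condition will be compared using an extra-sum-of-squares F-test".
- Demand indices: "each individual demand index will be compared across conditions using t-tests". The Outcome Measure section defines these as cigarillo indices and lists cross-price elasticity separately, as exploratory.
- Cigarillo count (primary) and total milligrams of combusted and non-combusted tobacco (secondary): random-effects models in which "Warning condition will be included as a between-subjects fixed effect".
- Exploratory regressions on condition: negative affect, elaboration, intentions and recall or recognition. Cross-price elasticity is not named.

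**The concern.** The promised conclusion is about an effect of the warning, while the stated measure is about an effect of price. A positive B1 says that people buy more of an alternative as cigarillos become dearer, which can happen equally in all three arms. Under the stated rule, a price response could be reported as substitution caused by the warning.

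The promise also reaches products that the measure cannot cover. B1 is defined for tobacco products in milligrams of nicotine. Food and drink contain none, and the log of zero is undefined.

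The study is meant to inform rulemaking on warnings. Whether a warning moves users to cigarettes or another product bears directly on that.

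**Working it through.** The plan gives no numerical figure for this analysis, so there is none to reproduce. The check asks whether B1 can carry a warning effect.

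**Algebra.** Suppose the control mean at price P is m(P) and the warning multiplies it by a constant c at every price. Then log[c·m(P)] = log c + log m(P). The whole change, log c, goes into B0 and B1 is unchanged. This holds for any c and any prices.

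**Inputs for an illustration.** The prices are the six under Interventions and Interactions: 0.25, 0.50, 0.75, 1.50, 3.00 and 6.00 dollars. In natural logs the mean is 0.155 (geometric mean 1.17 dollars) and the sum of squares about the mean is 6.923. Assumed: control mean 2·P^0.25, and a warning that raises average purchasing of one alternative by 30%. The control mean averages 2.155 units over the six prices, so the rise is 0.30 × 2.155 = 0.647 units per trip.

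**Formulas.** With x = ln P and y = ln(mean purchasing), B1 = Σ(x − x̄)y / 6.923. B0 at centred log price is the mean of y.

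| How the 30% rise falls | B1 | B0 | Change in B0 |
|---|---|---|---|
| Control | 0.250 | 0.732 | |
| Proportional at every price | 0.250 | 0.994 | +0.26 |
| Same extra units at every price | 0.191 | 1.009 | +0.28 |
| All at the three lowest prices (78% rise there) | 0.002 | 1.023 | +0.29 |
| All at the three highest prices (49% rise there) | 0.403 | 0.933 | +0.20 |

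B0 rises in all four shapes. B1 stays, falls, falls to about zero, or rises. For the same-units shape, rises of 10% and 50% give B1 of 0.23 and 0.17. With a 30% rise, control slopes of 0.10 and 0.40 become 0.08 and 0.30.

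**Simulation.** Assumed: 525 per arm (1,575/3, equal allocation), Poisson purchases, between-person coefficient of variation (CV) 1.0 or 1.5, and 2,000 runs per setting. Tests use participant-level standard errors.

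| Two-sided 5% test | Price slope common to all | Price slope varies (SD 0.3) |
|---|---|---|
| B1 difference, proportional shape | 4.7% to 5.5% | 4.6% to 5.0% |
| B1 difference, same units | 96.9% to 97.5%, all negative | 38.6% to 48.1%, negative in all but one run |
| B1 difference, lowest three prices | 100% | 100% |
| B1 difference, highest three prices | 100% | 98.1% to 99.9% |

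The condition effect averaged over prices rejects in 97.7% to 98.7% at CV 1.0 and 77.3% to 80.9% at CV 1.5, across all shapes and both slope settings.

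One caution applies to any repair. Suppose B0 is compared between arms using the residuals of lines through six arm means (8 residual df for two arms). With no true effect, that test rejects in 53% to 69% of runs, because the six means come from the same people. With participant-level standard errors it rejects in 4.5% to 6.3%.

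**Do the secondary models fill the gap?** The non-combusted model gives a randomized comparison for e-cigarettes and pouches together. The combusted total can hide a move from cigarillos to cigarettes if cigarillos are counted in it (assumed). Take 10 cigarillos at r mg each plus 5 mg from cigarettes, and let two cigarillos be replaced by 2r mg from cigarettes. The total is 10r + 5 before and 8r + (5 + 2r) after, so it does not change. Food and drink are in neither total.

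**The case against.** The strongest reply is that this is under-specification and not error. The trial is a three-group comparison, the cigarillo curves are fitted by condition, and the disputed sentence does not say that the answer comes from B1 alone. Nobody need pool the arms and credit the pooled slope to one of them. That is fair as a guess at intent, but a comparison of B1 by arm, the natural reading, would still miss a proportional rise and could point the wrong way.

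The secondary models, which rank above this analysis, already test condition on milligrams of tobacco, and the combusted total can be read beside the primary cigarillo count. That stands in part. What remains missing is any product-specific contrast and anything on food or drink. The masking example needs an exact offset in milligrams.

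The figures rest on assumed effects, shapes and variability, and the weekly budget is not modelled. This also stands. Power of the condition effect depends on spread: with the same 30% rise and price-slope SD 0.5 it is about 51% to 55% at CV 2 and 26% to 30% at CV 3. The B0 comparison is weaker in one extreme shape (highest three prices), at about 56% to 57% for CV 1.5. The high false-positive rate belongs to a B0 test that the plan does not propose; it matters only as a warning about how to make the repair.

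**Conclusion.** The concern holds. The plan states a conclusion about the warning that its stated measure cannot support, and for food and drink it describes no analysis at all. That a proportional rise leaves B1 unchanged is algebra and needs no assumption. The sizes in the tables are illustrations under assumed effects, equal allocation and no budget constraint.

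The consequence is limited. The analysis is exploratory, and the primary outcome, sample size and data collected are unaffected. The change should still be made, because an explicit policy conclusion lacks a supporting analysis and the repair is cheap.

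**What to change.** 1. Reword the sentence so that B1, reported for each arm, describes price-driven substitution only.
2. For each alternative, extend the plan's random-effects model to participant-level purchases, in milligrams of nicotine for tobacco and in units for food and drink. Use fixed effects for condition, log cigarillo price centred at its mean over the six trips (0.155, about 1.17 dollars) and their interaction, with participant-level robust standard errors. Report the condition effect averaged over the six prices, pictorial versus each text arm, with 95% intervals.
3. At minimum, fit the existing line by condition and report between-arm differences in both B0 (at centred log price) and B1, with intervals from resampling participants. Do not use the residual error of a line through six means.
4. Show these estimates beside the primary cigarillo contrast and its interval, and label them exploratory.

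The cost is SAP wording and a few more model runs on purchases already recorded. The drawback is multiplicity. Five outcomes (cigarettes, pooled e-cigarettes, pouches, drink, snack) by two contrasts make 10 tests, with 10 × 0.05 = 0.5 false positives expected if there are no effects. Keeping the three e-cigarette variations separate makes 7 × 2 = 14 tests and 0.7 expected.
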